#### Data Collection

All research personnel will be CITI-trained. A nursing student will assist the nurse researchers with data collection. Each data collector will undergo fidelity checks (performed by the PI) for each measurement procedure before they will be allowed to collect data. They will also be trained in using the ASA24-2016® dietary recall, so they can assist the patients as needed.

The current version of the YFAS, the YFAS 2.0, will be used to assess participants obesity phenotype (positive or negative for FA). This measure adapts the eleven DSM-5 diagnostic criteria for substance-related and addictive disorders when the substance is HPFS foods. In order to meet the diagnostic threshold on the YFAS, individuals must report at least two of the eleven diagnostic indicators of FA plus clinically significant impairment or distress.

The Automated Self-Administered 24-hour Recall, version ASA24-2016® will be completed at each time point to assess changes in patients dietary intake. This web-based 24-hour dietary recall instrument has been used effectively by hundreds of researchers and has face validity and similar intake results to the AMP.10 A strength of the ASA24-2016® is that it includes most traditional American foods/ingredients.

Height: The patients height will be used in determining BMI and BIA measures. We will use the average of 2 heights (cm) measured with the Seca EC0123 stadiometer. During measurement, patients will be in socked feet with heels placed against the back of the platform and facing straight forward.

Body Composition: Bioelectrical impedance analysis (BIA) will be used to determine body composition. Estimated standard error for BIA is  $\pm$  3.5-5%. We will use a Tanita SC-250 body composition analyzer and follow a standardized protocol to measure percent body fat, body fat mass, fat free mass, percent body water, muscle mass, bone mass, BMI, and visceral fat. The software also classifies patients as underfat, healthy, overfat, or obese based on percent body fat, age and gender.

Waist circumference: We will use the average of 2 measurements (cm) performed with the patient standing erect with their arms at their sides. Waist circumference will be measured at the uppermost lateral border of the right ilium at the end of normal expiration using an inelastic tape measure positioned around the trunk parallel to the floor. This measure is included because it is a better indicator of body fat and, therefore, health risk than

BMI: In addition, results of a recent study in this population demonstrated that waist circumference has potential as a means of identifying patients with or at risk for obesity and hypertension.

Blood Pressure: We will use the average of 2 blood pressure measurements performed using an Omron HEM- 907 automatic blood pressure monitor. The measurements will be performed while the patient is quiet and still using the appropriate sized cuff placed snugly around the upper arm approximately 2 to 3 cm above the antecubital fossa with the mark on the cuff aligned with the artery.

Determinants of Change Measures: MI Algorithm Questions: These reflect the PCBT determinants of behavior change (the patients perceptions toward limiting HPFS/increasing CC intake). They assess patient attitudes/beliefs (importance score), perceived norms (perceived barriers), and perceived behavioral control/self-efficacy (confidence score). These measures will be recorded by the interventionist nurses during each MI session for their assigned patients.

If a subject experiences success in managing their weight while participating in the study,(which will be determined by a 5% decrease in BMI or body fat or total body mass over 4 months) the subject may continue with the weight management plan after completing all study related visits. All participants may continue with clinic visits following the study and may have available to them, usual care, MI, Contrave (unless they have taken it in the study and it was not effective), and bariatric surgery options. All subjects taking Contrave will be screened at each visit for suicidal ideation. In addition, they will be asked to call [name] immediately if they have any such feelings or symptoms of suicidal ideation. If they present with suicidal ideation, [name] will interview them using the Suicide Screening Algorithm (see documents) to determine the severity of the symptoms and make additional medical referrals as necessary. If the case is emergent, they will be immediately escorted to the ER or asked to come into the ER, if it is a phone visit. . If the case is urgent, they will be referred to psychiatric personnel in the office where [name] practices as a Psychiatric NP. They will be withdrawn from the study at this time and

[name] will be notified. [name] will follow up with these patients. At the six month visit a PHQ-9 and the YFAS (from the WALI) will be readministered. An appt for a 12 month sustainability measure will be set up.

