#### Proposed methods/approach

Investigators propose assessing obese clients with the YFAS as part of their intake once they are referred to the Healthy Behaviors Clinic by Regional West physicians/practitioners. A nurse researcher with expertise in MI and a nurse practitioner will perform intake assessments, obtain consent and randomly assign participants in each phenotype (positive or negative for FA) to one of three treatment groups (usual care, individual MI alone, and individual MI with pharmacotherapy). Interventions will occur over 6 months. A clinical psychologist with expertise in the YFAS (University of Michigan) will serve as a consultant on this project and a registered dietitian (University of Nebraska Lincoln) will serve as a co-investigator.

Investigators expect that MI and MI+P and P will be more effective in improving outcome measures than IC. We also expect that response to the treatments will differ between the two obesity phenotypes (those testing positive and those testing negative for FA).

To determine if MI alone or MI+P or P is effective in treating obese patients with and without FA (based on the YFAS) as determined by :

- Higher MI confidence, importance and readiness to change scores
- Reduced intake of foods that are highly processed and high in fat and sugar (HPFS) and increased intake of complex carbohydrate foods(fresh fruits, vegetables, whole grains) and minimally processed proteins (nuts, fresh meats) (ASA24-2016® dietary recall)
- Improved biometric measures (BMI, body composition, waist circumference, and blood pressure)

-To determine whether the two obesity phenotypes (with and without FA) differ in their response to the four treatments.

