**Initial Screening for Eligibility (Suicidal Ideation, Pregnancy test (urine test), Lactation, Recruitment):**  
Participants will be recruited from obese patients referred to the Healthy Behaviors Clinic by Regional West Physicians. Nurse researchers who work at the Healthy Behaviors Clinic will inform potential participants about the study and, if they agree to participate, will consent them.

Both treatment groups, Those who test positive for and those who test negative for FA (food addiction) will be assigned to one of four treatment arms, IC, MI, MI+P and P. All will receive dietary and exercise information. After consenting, each participant will be administered the YFAS to determine their obesity phenotype (positive or negative for FA). Participants within each phenotype will be randomly assigned to one of the intervention (MI or MI+P, or P) or the IC information control (diet and physical activity instruction, which will be no less than current standard of care) treatment groups using a randomization schedule (assignments in numbered, sealed, opaque envelopes; one set for each phenotype) 1:1:1:1 ratio, provided by our statistician, [name]. Phenotype assessment and treatment assignment will continue until the sample size (n=10) is met for each phenotype-treatment group category. Those in the control group will be seen at the same time periods as each treatment group to maintain their interaction time with the clinic. They will receive diet and exercise instruction at each time point.

**Intervention Conditions (MI, MI+P):** MI is theorized to decrease a patient's ambivalence and increase his/her perceived behavioral control (self-efficacy) for limiting HPFS and increasing CC intake by emphasizing personal choice and control in decision-making and by affirming the patient's self-management ability. Interventionist nurses will deliver MI sessions following data collection at baseline, 1, 2, 3, and 4 weeks and 2, 3, 4, 5, and 6 months to promote sustained behavioral change. A written MI algorithm will be used to ensure uniform implementation of the intervention.

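### Outcome assessment is not masked: the nurse researchers who assign patients also collect outcomes, so tape waist and assisted dietary recall could lean towards the arms expected to do better

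*Combined protocol and SAP*

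**What the plan says.** On assignment, Proposed methods/approach states: "A nurse researcher with expertise in MI and a nurse practitioner will perform intake assessments, obtain consent and randomly assign participants". The section on initial screening adds that nurse researchers working at the clinic inform and consent patients, and that allocation comes from numbered, sealed, opaque envelopes.

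On measurement, Data Collection states: "A nursing student will assist the nurse researchers with data collection". Data collectors are also trained in the ASA24 dietary recall "so they can assist the patients as needed". Waist circumference is the mean of two readings taken "using an inelastic tape measure positioned around the trunk parallel to the floor". Body composition comes from a bioelectrical impedance (BIA) analyser and blood pressure from an automatic monitor.

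On treatment, the intervention text states: "Interventionist nurses will deliver MI sessions following data collection at baseline", with sessions at nine later time points as well. On the MI importance and confidence scores, Data Collection states: "These measures will be recorded by the interventionist nurses during each MI session for their assigned patients".

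On expectation, Proposed methods/approach states: "Investigators expect that MI and MI+P and P will be more effective in improving outcome measures than IC".

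Masking, placebo and an independent outcome assessor are not mentioned anywhere.

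**The concern.** Patients know whether they receive tablets, MI, both, or information only, and that cannot be changed in this design. Whether the person holding the tape or helping with the recall also knows is a choice, and the plan leaves it open. The staff group that learns the allocation is the group that measures, and the direction of the expected result is written into the protocol.

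The sample size justification says the pilot will focus on description, effect-size estimation and hypothesis generation. A systematic lean in measurement goes straight into those effect sizes. Unlike random error, it does not shrink with more patients, and it would be carried into the planning of any larger trial.

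**Working it through.** **Step 1. Who does what**

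| Task | Staff named | Section |
|---|---|---|
| Consent and random assignment | Nurse researcher with MI expertise, nurse practitioner; clinic nurse researchers also consent | Proposed methods/approach; initial screening |
| Outcome measurement, ASA24 help | Nurse researchers, with a nursing student; all data collectors trained to help | Data Collection |
| MI sessions | Interventionist nurses, after data collection at the visit | Intervention Conditions |
| MI importance and confidence scores | Interventionist nurses, for their own patients | Data Collection |

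The first two rows share a staff group. The overlap of treating and measuring is explicit only in the last row.

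**Step 2. What the safeguards cover**

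- Sealed envelopes protect the assignment, not later measurement.
- Fidelity checks take place before a collector starts. They test technique and do not hide the arm.
- A fixed waist landmark and the mean of two readings limit latitude and random error. They do not remove a lean shared by both readings.
- Patients taking the study drug are screened for suicidal ideation at each visit, a further cue to the arm.

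**Step 3. Risk by outcome**

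- Tape waist: read by hand, so open to expectation in any arm.
- ASA24: web-based and self-administered, but self-reported, with staff help where needed.
- MI scores: elicited and recorded by the treating nurse, so unmasked by construction.
- BIA and blood pressure: read by a device, so low risk.

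**Step 4. The plan's own figure**

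The planning inputs are f = 0.25, alpha 0.05 and power 0.95, with a stated total of 252. Noncentral F power with noncentrality f²N gives 252 for three groups (power 0.951) and 280 for four. That discrepancy is a separate matter. Only the planning f of 0.25 is used below.

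**Step 5. Illustration of a lean (assumed, not from the documents)**

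Take four equal groups with no true effect, IC at 0 and each active arm shifted by b SD. The grand mean is 3b/4, and the variance of the group means is [(3b/4)² + 3(b/4)²]/4 = 3b²/16. So f = b√3/4 = 0.433b.

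- b = 0.2: f = 0.087; 0.087/0.25 = 35%
- b = 0.4: f = 0.173; 0.173/0.25 = 69%

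In centimetres, if the SD of waist change is 5 cm, a lean of 1 to 2 cm is 0.2 to 0.4 SD. If the effect is standardised instead by an assumed between-patient SD of 12 to 16 cm, 1 to 2 cm is 0.0625 to 0.167 SD. Then f = 0.433 × 0.0625 = 0.027 up to 0.433 × 0.167 = 0.072, or 11% to 29% of 0.25.

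**Step 6. Effect on tests**

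With zero true effect and a two-sided 5% t-test of one active arm against IC (noncentrality b√(n/2)):

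| Lean | 10 per arm | 5 per arm (50% attrition) |
|---|---|---|
| 0.2 SD | 7.1% | 5.9% |
| 0.3 SD | 9.7% | 7.1% |

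The inflation of the error rate is modest at pilot size. In a four-group trial of 252, the same leans, shared by the three active arms, would alone reject in 18% and 37% of trials. The harm is mainly to the estimates and to what is later built on them.

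**The case against.** The strongest reply is that much of this is silence in the plan rather than documented bias, and several parts of that reply stand.

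- A reader might infer that the nurses who treat are the nurses who measure. The documents do not say so: treatment is given by interventionist nurses and measurement is by nurse researchers, a student and data collectors. Identity is likely, given a nurse researcher with MI expertise and shared visits, but it is not stated. The point does not need it, because knowing the arm through assignment is enough.
- A reader might infer that assisted recall favours all three active arms over IC. The documents do not support this for P, for which no MI session is described. IC patients also receive advice to limit HPFS foods, at the same time points and in sessions of similar length, so pressure to under-report exists there too and may partly cancel. A differential remains plausible for MI and MI+P against IC.
- A reader might convert f = 0.25 to d = 0.5 and put the lean at 40% to 80% of the planned effect. That is the two-group conversion. It does not fit three leaning arms against one control, which gives 35% to 69% for the same assumed lean.
- The fixed waist protocol, the fidelity checks and the device-read outcomes narrow the risk. They do not mask the arm for tape waist or assisted recall.
- Patients know their arm whoever helps them, so a different helper removes only part of any recall bias.

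The pilot's descriptive purpose does not answer the point, since effect sizes are its stated product.

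**Conclusion.** The point holds as a risk that the plan leaves open and could reduce with its own staff. No masking of outcome assessment is described, the group that assigns patients also collects outcomes, and nothing separates the two roles for an individual patient. The exposed outcomes are tape waist and staff-assisted ASA24 recall. The MI importance and confidence scores are unmasked by design.

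The size cannot be derived from the documents. The 35% to 69% of the planning f rests on an assumed lean of 0.2 to 0.4 SD shared equally by MI, MI+P and P. That pattern suits the tape reading better than the recall, and a smaller lean gives proportionately less. The supportable conclusion is that effect sizes could be inflated, not that they will be.

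**What to change.** Amend Data Collection so that the nursing student, or a data collector who neither assigned nor treats that patient, measures waist and gives any ASA24 help. This should happen before the session, on a form that does not show the arm, and without access to the MI form or drug record. Data collection already precedes the MI session, so the visit order stands.

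State in the same section that the MI importance and confidence scores are recorded unmasked by the treating nurses, and interpret them accordingly. Where separation of roles proves impossible, declare the assessment unmasked and give more weight to the BIA and automatic blood pressure results.

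The cost is a scheduling constraint across ten visits (baseline, four weekly and five monthly), with no new staff or procedure. Masking will be imperfect, because patients may reveal their arm.

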MI will be operationalized by the nurse asking the patient about his/her knowledge, limiting HPFS/increasing CC and natural fat intake, defining FA, and explaining why it is important to limit their HPFS/increase their CC and natural fat intake. The nurse will ask the patient to rate the importance of limiting HPFS/increasing CC and natural fat intake (scale of 1-10) and their confidence in their ability to do so (scale of 1-10). The nurse will focus on the lower score and ask the patient why they chose that score and what they thought it would take to increase the number. If the patient rates the importance of understanding of limiting HPFS/increasing CC and natural fat intake low, the nurse will provide information on the benefits of limiting HPFS/increasing CC and natural fat intake to reduce their risk of obesity, diabetes, heart disease, and numerous other co-morbidities associated with overweight. If the patient rates their confidence in their ability to limit HPFS/increase CC and natural fat intake as low, the nurse will provide the patient with strategies to decrease barriers and increase confidence, such as a list of healthy snack food choices, stepped changes (3 sodas per day to 2 sodas and 1 water per day, etc.), and having the patient choose healthy foods at the store. The same questions will be asked at each time point.

Nurse responses will be tailored to the specific motivational issues of each individual patient at each time point. During each session, the nurse will document the patients responses to the MI algorithm (levels of confidence, importance, and readiness to change), their perceived barriers and concerns, and suggestions to address them/setting achievable goals. The MI documentation form will ensure that all nurses collect the same data and provides a record that the nurses can reference during their sessions to help them adjust each MI session to the patients' individual needs. If a patient reveals a new barrier that is not included in the training materials, the nurses will meet with team members to discuss the new barrier and strategies to address it will be shared with all interventionists.

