In the group with pharmacotherapy added to the MI, the naltrexone-bupropion (Contrave) protocol will be added to the patients intervention. Dosing protocols will be followed for treatment of obesity: Orally, 1 tablet (90mg/8mg) initially week 1; increase by 1 tablet/day each subsequent week until daily maintenance dose of 2 tablets twice daily (360 mg bupropion/32 mg naltrexone) is achieved at the start of week 4. Use will be discontinued at month 4 if no clinical response is observed. This drug (Contrave) is to be taken with a high fat meal.

In the pharmacotherapy group alone, dosing protocols will be followed for treatment of obesity: Orally, 1 tablet (90mg/8mg) initially week 1; increase by 1 tablet/day each subsequent week until daily maintenance dose of 2 tablets twice daily (360 mg bupropion/32 mg naltrexone) is achieved at the start of week 4. Use will be discontinued at month 4 if no clinical response is observed. This drug (Contrave) is to be taken with a high fat meal.

The IC control group will receive diet and physical activity information to encourage them to adopt healthier eating (limit HPFS/increase CC intake) and physical activity behaviors. IC information sessions will occur at the same time points as the intervention sessions (baseline, 1, 2,3, and 4 weeks and 2, 3, 4, 5, and 6 months) and will be similar in length. The PI and co-PIs will develop information packets for each session, (self-management, avoiding highly processed LNSC foods, low intensity physical activity, avoiding highly processed fatty foods, medium intensity physical activity, avoiding LNSC beverages, importance of water as a beverage to hydrate and reduce cravings, avoiding high fat beverages, high intensity physical activity, importance of CC intake).

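### Motivation scores, the first-listed outcome, are collected only in motivational interviewing sessions, so no comparison with the control arm is possible on them

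*Combined protocol and SAP*

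**What the plan says.** Under Proposed methods/approach the aim is stated as: "To determine if MI alone or MI+P or P is effective in treating obese patients with and without FA". The first criterion listed is: "Higher MI confidence, importance and readiness to change scores". The same section gives the direction expected: "Investigators expect that MI and MI+P and P will be more effective in improving outcome measures than IC". Statistical Methods to Analyze Data then plans an analysis of variance of these scores between treatment groups, in the same sentence as dietary recall and the biometric measures.

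Collection is described in two places, both inside MI delivery:

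- The text on the intervention conditions, under Initial Screening for Eligibility, makes the questioning part of the technique: "MI will be operationalized by the nurse asking the patient about his/her knowledge". The importance and confidence ratings (1 to 10) follow, and the nurse then works on whichever is lower. On recording it says: "During each session, the nurse will document the patients responses to the MI algorithm (levels of confidence, importance, and readiness to change".
- Data Collection, under Determinants of Change Measures, says: "These measures will be recorded by the interventionist nurses during each MI session for their assigned patients".

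For the control arm the plan says: "IC information sessions will occur at the same time points as the intervention sessions". The content of those visits is diet and physical activity information. The P arm is described by its dosing, plus the diet and exercise information that every arm receives.

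**The concern.** The outcome is defined for all four arms but measured only where MI is delivered. An effect of MI, MI+P or P against control needs control values, and the written procedure yields none. Scores that were not asked for at baseline and follow-up cannot be recovered later.

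There is a second problem within the arms that do have scores. The patient gives the rating face to face to the nurse delivering the treatment, and the rating steers what that nurse does next. The measurement is part of the intervention. Without a control arm measured in the same way, a rise over time cannot be separated from the passage of time, attention, or a wish to please the nurse.

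**Working it through.** The plan gives no figure for this point, so the check is a count of where scores would exist, followed by what could be estimated.

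**1. Which arms would have scores**

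| Arm | MI sessions? | Provision for collecting the scores |
|---|---|---|
| IC | No | None stated |
| MI | Yes | Each MI session |
| MI+P | Yes | Each MI session |
| P | No | None stated |

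MI sessions fall at baseline, weeks 1 to 4 and months 2 to 6, which is 10 occasions. The statement that the same questions are asked at each time point closes a paragraph about conducting MI, so it does not reach IC or P.

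**2. How many patients**

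- Initial Screening for Eligibility: 1:1:1:1 allocation and 10 per phenotype-treatment category. Per phenotype: 4 × 10 = 40 patients, of whom IC + P = 2 × 10 = 20 have no score. Over both phenotypes: 8 × 10 = 80 patients, of whom 4 × 10 = 40 have none.
- The sample-size paragraph: 40 enrolled, 10 per group. IC + P = 20 of 40.

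The two sections disagree on the total, but the share without scores is 50% under either.

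**3. Which contrasts survive**

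| Contrast | Score data | Estimable? |
|---|---|---|
| MI vs IC | MI only | No |
| MI+P vs IC | MI+P only | No |
| P vs IC | Neither arm | No |
| MI vs MI+P | Both arms | Yes |

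So 3 of 3 contrasts with IC are lost.

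**4. Can the planned analysis work around this?**

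- *Analysis of variance.* The statistical section refers to three treatment groups without naming them. Only two arms have scores, so any three of the four include IC or P. The three arms listed under Proposed methods/approach (usual care, MI, MI+P) include the control.
- *Imputation.* The EM algorithm or multiple imputation is to be considered. With every IC score missing, at baseline and at follow-up, the data hold nothing about the IC mean. Imputed values would come from the MI arms and would carry an assumption about the treatment effect in place of an estimate.
- *Aim 2.* The t-test of FA-positive against FA-negative patients can be run on these scores within MI and MI+P, but not within IC or P.

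**5. What collection in all arms would give**

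For a difference between two arms of n patients each, the 95% confidence interval half-width in SD units is t(0.975, 2n − 2) × √(2/n):

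| n per arm | Situation | Half-width |
|---|---|---|
| 20 | Both phenotypes pooled, no attrition | 0.64 SD |
| 10 | One phenotype, no attrition; or pooled with the 50% attrition allowed for | 0.94 SD |
| 5 | One phenotype with 50% attrition | 1.46 SD |

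These are wide, as expected in a pilot, but they are estimates. The current procedure gives none.

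**The case against.** The strongest reply is that the plan never says IC and P patients will not be asked. The scores sit in the planned between-group analysis beside diet and biometrics, and IC visits match the MI schedule, so the investigators may have meant to collect them everywhere. That is possible, and the exact statement is that the plan provides for no collection in IC or P. But the Data Collection section is what staff will work from, and following it produces no scores in those arms.

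It can also be said that this is a pilot, that no primary outcome is named, and that diet and biometric outcomes are unaffected. The last two are true: one of the three outcome groups listed is hit. Pilot status does not help, because the sample-size paragraph makes estimation of effect sizes a purpose, and an effect size against control needs control data.

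Three practical points stand and shape the fix. The rating questions are part of MI, so asking them in IC and P exposes those arms to a fragment of it; the documents do not allow the size of that effect to be judged. The P arm has no visit schedule of its own written down, although dietary recall is due at each time point and patients on drug are screened at each visit. Readiness is to be documented, but only importance and confidence are given a scale.

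**Conclusion.** The concern holds. As written, the plan cannot compare any active arm with IC on confidence, importance or readiness: 2 of 4 arms lack all three scores and 3 of 3 contrasts with control are not estimable. In patients this is 40 of 80 at 10 per phenotype-arm cell, or 20 of 40 on the sample-size paragraph's total. The one comparison of arms left, MI against MI+P, concerns adding drug to MI and does not show whether MI works.

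This assumes that staff follow the written procedure and that no unpublished form extends the questions to IC and P. It must be settled before enrolment, because missed baseline ratings cannot be recovered.

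**What to change.** Take the importance, confidence and readiness ratings out of the MI conversation and put them in the data-collection step that precedes each session. Have a data collector administer them, or let patients complete them alone, with identical wording in all four arms at baseline and every scheduled time point. The MI nurse then uses the recorded scores in the session. Define the readiness item and its scale, state the P arm's assessment times, and name all four arms in the analysis of these scores.

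The cost is three short questions at contacts that already exist, with no extra staff. The drawback is that the questions may prompt some reflection in IC and P, which would make an MI effect somewhat harder to show. If that is a worry, asking IC and P only at baseline and 6 months would limit it and still fit the pre-post design, at the price of the intermediate comparisons.
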